8.3.2 Interim Analyses

This study has an internal pilot with analyses to be conducted at 6 months to assess if the full RCT should proceed. The primary criteria of acceptability are:

- i. Percent of trial recruitment complete
- ii. Recruitment rate/site/month
- iii. Number of GP practices opened
- iv. Total number of participants recruited

Pilot data will be presented in grouped tables with frequency and percentages for the 4 criteria so that it can be determined if the study fulfils the criteria for progression.

The IDMC and its delegates will have unrestricted access to unblinded data and will direct the unblinded statistician to provide reports as they require.

TSC reports will be provided as requested. The contents of the report will be determined by the TSC.

There are no other prespecified interim analyses planned for the duration of the study and assuming that permission is granted to proceed to a full RCT unless requested by the IDMC or TSC

8.3.3 Statistical Methods – Outcomes

The primary analysis will be a generalised mixed model with identity link and Gaussian / mixed error structures, with log(e) GAD7 scores at 12 weeks as the outcome, accounting for baseline GAD7 scores using a repeated measures framework and also including minimisation factors used in the randomisation process. Natural logarithms will be used following our previous experience with the PANDA study(Lewis *et al.*, 2019) that suggested it was more efficient, and evidence that minimal clinically important differences for scales such as GAD fit a geometric model more closely. There will be two observations for each participant, the baseline and 12-week scores. These will be linked within a participant using a random intercept term. The model will be parameterised to identify baseline and post randomisation observation as one parameter, and random allocation as the second parameter. For the latter, all baseline measures will be coded as no treatment, and the post randomisation values will be classified as active or placebo. We will not make adjustments for repeated testing but will discuss the possibility that type 1 errors would have increased in the discussion.

Secondary analyses will choose the appropriate analogous generalised mixed model, for the outcome and account for the baseline measurement of the outcome. We will describe randomised groups at baseline. Summary statistics for continuous variables will be mean, median, SD, lower quartile, upper quartile and reported appropriately according to distribution. Summary statistics for binary and categorical variables will be n (%).

We will carry out supportive analyses including the minimisation variables as explanatory variables. We will also investigate baseline variables associated with missing outcome data for the primary outcome. We will carry out mediation analyses to examine the influence of missingness. All principal analyses will be complete case, intention to treat (defined as all patients randomised, analysed according to their randomised group regardless of treatment received). Although we will minimise missing data by trial conduct (building on the considerable experience and success of the team on previous studies) we will investigate the potential impact of missing data on the primary objective through threshold analyses which will impute a poor outcome for missing pregabalin patients while assuming an average outcome for missing control patients.

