3.1 Participant Inclusion Criteria

1. Meeting ICD-11 criteria for generalised anxiety disorder using the revised clinical interview schedule (CIS-R)
2. Scoring ≥ 12 on the CIS-R total score
3. Age 18-74 years (upper age limit to ensure the validity of our measures)

4. Currently taking an SSRI, SNRI or mirtazapine (at specified doses; the full list is in the trial guidance document that all investigators at sites have to follow), for a minimum of 8 weeks prior to randomisation and with good adherence as agreed with PI.
5. Treatment with at least one other antidepressant before their current antidepressant

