3.3 Recruitment

General practices, who have agreed to take part, across 4 geographical areas: London, Bristol, North West Coast and West Midlands, will carry out record searches to identify people who have been prescribed an antidepressant for at least 8 weeks and will contact potential participants with the participant information sheet and ask those interested to contact the

research team by all possible means, including a weblink. The initial contact will be via post, although GP practices may also text patients with a reminder to respond to the invitation letter. GPs and other primary care clinicians will also be invited to refer directly to the study team with patient agreement. A trained research assistant will then establish by phone some of the eligibility and exclusion criteria and screen with a GAD7 questionnaire to assess anxiety symptoms. This GAD7 screen will not be part of the eligibility criteria but is designed to increase the likelihood that participants will meet our eligibility criteria when they are assessed at the baseline visit. It is designed to improve the efficiency of the fieldwork. The consent will be obtained for the assessment of eligibility, supplemented by details from medical notes such as concerning renal impairment. For those potentially eligible for the trial, a baseline assessment will be performed online, or face to face in a general practice or at home or at University premises to establish eligibility.

We recognise that general practice is under considerable pressure at present, and we have designed this study to have minimal impact on the practice. For example, UCL and University of Bristol will be the Investigator sites (with Keele University acting as a co-ordinating centre for UCL participants recruited in the West Midlands region) and the practices will be research sites with no PI oversight required, this will minimise the paperwork for the practice.

We plan a 6-month internal pilot to estimate our recruitment rate and test the robustness of our procedures. The internal pilot will occur at the UCL site only so we can adapt and finalise any procedures before opening the University of Bristol site and activating the Keele University co-ordinating centre for UCL participants recruited from the West Midlands and North West Coast. Table 2 shows the internal pilot progression criteria.

Table 2. Internal pilot progression criteria

Progression criteria	Red	Amber	Green
Trial recruitment % complete	50%	70%	100%

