8.3.6 Analysis Population and Missing Data

Outcomes will be analysed by means of Generalised Mixed Models without imputation of missing data. Measurements within individuals will be linked using a random intercept term. We will use two timepoints for the final analysis; baseline and primary timepoint at 12 weeks. An Intention-To-Treat (ITT) analysis will be carried out by randomisation group irrespective of medication compliance. The analysis population will consist of all those participants who were randomised. Mechanisms of missingness will be explored. The principal analyses will address a treatment strategy estimand, except death which will be while alive.

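### The primary model's random-intercept link assumes equal variance of ln(GAD7) at baseline and 12 weeks; if the 12-week variance is larger, as is likely when scores fall, the primary standard error is too small

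*Protocol*

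**What the plan says.** Protocol section 8.3.3 sets out the primary model in some detail: "The primary analysis will be a generalised mixed model with identity link and Gaussian / mixed error structures, with log(e) GAD7 scores at 12 weeks". It continues: "There will be two observations for each participant, the baseline and 12-week scores". The covariance between the two is then given: "These will be linked within a participant using a random intercept term". Section 8.3.6 repeats it: "Measurements within individuals will be linked using a random intercept term".

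The mean structure is a common baseline mean with treatment acting only at follow-up, since "all baseline measures will be coded as no treatment, and the post randomisation values will be classified as active or placebo".

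Neither section mentions a residual variance that differs by visit, an unstructured covariance or a robust standard error. The phrase about Gaussian / mixed error structures is not defined.

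On who enters, section 3.1 requires an ICD-11 diagnosis of generalised anxiety disorder by the CIS-R and "Scoring ≥ 12 on the CIS-R total score". It sets no GAD7 threshold, and section 3.3 is explicit: "This GAD7 screen will not be part of the eligibility criteria but is designed to increase the likelihood that participants will meet our eligibility criteria".

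**The concern.** A random intercept with a single residual variance gives both visits the same total variance, namely the intercept variance plus the residual variance. The fit therefore averages the baseline and 12-week variances. The treatment effect, however, is a contrast of 12-week scores, and its sampling error depends on the 12-week variance. If 12-week scores are more spread out than baseline scores, the average is too small, the confidence interval too narrow, and the 5% test rejects too often.

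Two features of the trial point that way. Participants are selected on a current diagnosis and on symptom severity, which may narrow baseline scores. More important, the analysis is on the log scale, where a fall in mean score moves participants into the region that the logarithm stretches.

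At stake is the trial's single primary test, with the likely error in the direction of a false claim of benefit. Section 8.3.3 says that secondary analyses will use analogous models, so the continuous secondary outcomes would inherit the same assumption.

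**Working it through.** **Inputs from the protocol (section 8.1).** Raw-scale SD 5.6 or 5.8, from earlier trials at 6 months; correlation of baseline with 12-week GAD7 0.47; difference 1.6; 199 per group; 90% power; 5% significance; 20% attrition; total 498. No baseline SD and no log-scale SD is given. Two-sided testing is assumed.

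**The plan's own figures.** Effective SD = 5.6 × sqrt(1 − 0.47²) = 4.94, stated as 4.9. Per group, n = 2 × (1.960 + 1.282)² × 4.9²/1.6² = 197.1, so 198 by the normal formula; with the t distribution, 199 gives 90.1% power. Total 398/0.8 = 497.5, so 498. The sample size reproduces. It rests on follow-up SD × sqrt(1 − r²), the residual SD of an ANCOVA, and not on an average of the two visits' variances.

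**Standard error under the stated model.** Let SD0 and SD12 be the SDs of the log score at the two visits (after any covariates), c their covariance, v = (SD0² + SD12²)/2 and b = c/v.

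- The variance that the model reports is proportional to v − c²/v = v(1 − b²).
- The true variance of the same estimator is proportional to SD12² − 2bc + b²SD0². Putting c = bv, this is SD12² − b²(SD0² + SD12²) + b²SD0² = SD12²(1 − b²).
- Hence reported SE / true SE = sqrt(v)/SD12. The correlation cancels.

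With k = SD0/SD12, the ratio is sqrt((k² + 1)/2), and type I error = 2 × (1 − Φ(1.96 × ratio)). For k = 0.8: sqrt(1.64/2) = 0.906; 1.96 × 0.906 = 1.775; type I error 7.6%.

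| k (assumed) | SE ratio | Type I error |
|---|---|---|
| 1.25 | 1.132 | 2.7% |
| 1.1 | 1.051 | 3.9% |
| 1.0 | 1.000 | 5.0% |
| 0.9 | 0.951 | 6.2% |
| 0.8 | 0.906 | 7.6% |
| 0.7 | 0.863 | 9.1% |
| 0.6 | 0.825 | 10.6% |
| 0.5 | 0.791 | 12.1% |

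Simulation of Gaussian scores (6,000 null trials per setting, 199 per arm, correlation 0.47) gave 2.7% at k = 1.25, 4.8% at 1.0, 8.1% at 0.8, 10.6% at 0.6 and 12.7% at 0.5. ANCOVA on the same data gave 4.7% to 5.3%.

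**What k might be on the log scale.** This needs assumptions: rounded scores limited to 0–21, correlation 0.47 before rounding and limiting, no baseline cut-off, the same mean change in both arms, and ln(score + 1), because ln(0) is undefined and the protocol names no offset.

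| Assumed raw means and SDs | Log-scale k | Type I error, random intercept | ANCOVA |
|---|---|---|---|
| 12 to 12; SD 5.6 at both visits | 1.0 | about 5% | about 5% |
| 12 to 9; SD 5.6 at both visits | 0.77 | about 8% (7.4% and 8.3% in two runs; formula 8.0%) | about 5% |
| 13 to 9; SD 4.5 then 5.6 | 0.51 | 12.0% | 5.4% |
| 13.5 to 9; SD 4.5 then 5.6 | 0.48 | about 13% | about 5% |

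The second row matters most. It has no restriction of baseline and equal raw SDs, and the log transform alone produces the unequal variances once the mean falls.

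**The case against.** The strongest reply is that the quoted text is not wrong in itself. A random intercept combined with visit-specific residual variances satisfies it, and for two visits that model is equivalent to an unstructured covariance. Neither section says that the residual variance is common to both visits, the phrase on error structures leaves some room, and the unseen statistical analysis plan may specify the variances. This stands in part: the protocol permits a sound model. But it goes well beyond leaving the model to the analysis plan. It names the covariance term twice, adds nothing about variance, and describes a model whose ordinary fit has one residual variance. An undefined phrase does not supply the missing term.

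The second reply is that the direction of the error is not established, and this stands. The only SDs given are on the raw scale, from other trials at 6 months. A reader might infer from the entry criteria that baseline GAD7 is range-restricted by eligibility. The document does not support that as fact: the severity threshold is on the CIS-R, a different instrument, and section 3.3 says that the GAD7 screen is not an eligibility criterion. Any narrowing of baseline GAD7 is indirect and of unknown size.

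Third, Table 5 describes a population that has not responded to at least two antidepressants, so scores may fall less than assumed above and fewer may come near zero. That would bring k closer to 1. It is a fair reason to read the 12% to 13% figures as illustrations and not as forecasts.

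**Conclusion.** The point holds in conditional form. As ordinarily fitted, the stated model gives a correct primary standard error only if ln(GAD7) has equal variance at both visits, and the protocol neither states nor supports that assumption. If the 12-week variance is larger, which the log scale makes likely when scores fall, the test is anti-conservative: 6.2% at an SD ratio of 0.9, 7.6% at 0.8, 9.1% at 0.7 and 12.1% at 0.5. The illustrative score distributions with a falling mean give about 8% to 13%, against about 5% for ANCOVA.

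A reader might go further and say that the trial's type I error does exceed 5%. The document does not show that. At equal variances it is 5.0%, with a larger baseline variance it is below 5%, and the ratio is unknown until data are seen. The illustrations also depend on the assumed means, SDs and offset. What can be said is that the error rate rests on an unstated assumption that is doubtful on the chosen scale and easy to remove.

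**What to change.** In sections 8.3.3 and 8.3.6, keep the repeated-measures framework and the common baseline mean, and add that residual variance may differ by visit: a random intercept plus visit-specific residual variances, equivalent to an unstructured 2×2 covariance. Alternatively, specify ANCOVA of the 12-week log score on the baseline log score. Define or delete the phrase on mixed error structures. Apply the same choice to the analogous continuous secondary models. If the statistical analysis plan already allows for visit-specific variances, bring the protocol into line with it.

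The cost is one sentence and one option in the model code. The estimand and the sample size do not change; the sample-size formula already matches an analysis that uses the follow-up variance. The change should be made before unblinding, because a covariance structure chosen afterwards would be open to the charge of having been chosen on the result.

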If a participant experiences intolerable side effects, the dosage may be decreased to the previous dose level at any time during the double-blind period and will be documented. The GP will be informed of any dose changes.

In cases where participants have missed doses, these should be reviewed and discussed by the investigator at the research site to advise on the best dosing plan to remain on trial medication. Participants who discontinue study medication will be invited to all follow up assessments. Once participants have discontinued study medication, they will not be able to re-commence.

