5.1.2 Secondary Outcomes

Anxiety and Depression

- Anxiety scores (GAD7) at week 3, week 6, week 26 and week 30.
- Dichotomised anxiety scores (present or absent based on a cut-off of GAD7 ≥ 10) at week 3, week 6, week 12, week 26 and week 30.
- Depressive scores (PHQ9) (Gilbody *et al.*, 2007) at week 3, week 6, week 12, week 26 and week 30.
- Panic symptoms (Spitzer, 1999)

Global Improvement & Quality of Life

- EQ5D5L (Herdman *et al.*, 2011) & SF-12 (Brazier and Roberts, 2004) at week 3, week 6, week 12, week 26 and week 30

Adherence

- Adherence to study medication will be assessed using a single item asking if they are still taking study medication and a 5-item scale used in the MIR and Cobalt studies. (Wiles *et al* 2013; Kessler *et al* 2018)

Withdrawal & Adverse Events

- Adverse effects of pregabalin and antidepressants – based on the Toronto scales for antidepressants (as used in GENPOD study (Crawford *et al.*, 2014)) with additional symptoms of pregabalin side effects (including waist circumference) and pregabalin withdrawal
- Withdrawal symptoms from pregabalin – these are included in the adverse effect scale above
- Stopping the study medication

Use of alternative anxiolytic methods

- Alcohol consumption (AUDIT PC) measured at every visit (Gómez *et al.*, 2005)
- Benzodiazepine use measured at every visit

Resource Use and Employment

- Primary care resource use (6 months pre and post randomisation)
- Antidepressant medication collected from primary care medical records (6 months pre and post randomisation)
- Self-reported health resource use (baseline and 26 weeks asking about previous 6 months) including psychological therapies.
- Self-reported social care resource use (baseline and 26 weeks asking about previous 6 months)
- Employment and time off work (baseline and 26 weeks asking about previous 6 months)

Cognitive Assessments

- Exploratory Assessments of reinforcement learning, working memory and general cognitive function (administered through a web browser using the Gorilla platform)

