8.3 Statistical Considerations

8.3.1 Estimand Framework & Statistical Analysis Plan

Table 5. Estimand Framework

Characteristic of estimand	Definition and method of analysis
Population	Participants who have a diagnosis of generalised anxiety disorder, who have not responded to at least two antidepressant

	medications, who are currently still taking antidepressant medication, who are in the community, who agree to enter the trial and who do not fulfil exclusion criteria.
Treatment conditions	Pregabalin medication versus placebo in addition to care as usual
Endpoint	Natural log of the score on the Generalised Anxiety Disorder scale at 12 weeks post randomisation
Summary measure	Mean difference between natural log of the score on the Generalised Anxiety Disorder scale at 12 weeks post randomisation between those randomised to placebo versus those randomised to pregabalin (adjusting for baseline scores).
Intercurrent Events	
 i. Death before outcome While alive policy ii. Withdrawal from randomised medication (stays in trial) Treatment policy iii. Withdrawal from medication (leaves trial) While in trial policy iv. Increased use of alcohol Treatment policy v. Psychiatric admission Treatment policy vi. Commencement of psychological therapies Treatment policy

Statistical Analysis Plan

A separate Statistical Analysis Plan will be pre-specified which will be held within the Statistics Master File (SMF). It will contain following sections:

- I. Introduction
- II. Study Methods
- III. Statistical Principles
- IV. Trial Population
- V. Analysis of Primary and Secondary Outcomes (including statistical models and method of dealing with missingness)

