8.3.4 Additional Analyses - Subgroup

Subgroup analyses will be described for the primary outcome. We will calculate interactions between randomised groups and each subgroup variable (below). Other variables in these models will be the same as those included in the main analyses of the primary and secondary outcomes. The subgroups investigated will be: class of antidepressant medication at baseline

(SSRI, SNRI, other), baseline anxiety score (median GAD7 total score at baseline), and baseline depression score (median baseline total score PHQ9).

The principal approach we will take to analysing the withdrawal symptom phase of the study will, in principle, use the intention-to-treat principle and therefore regard the original randomised sample as the population of interest. However, we recognise that attrition could affect the interpretation of the comparison between active and placebo, especially if differential between the groups. We will therefore carry out supportive analyses to examine the likely impact of attrition including the potential use of mediation analyses and joint models.

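### Section 8.3.3 uses mediation analysis to examine missing week-12 GAD-7 but names no mediator, and none of the evident choices shows how missing outcomes affect the treatment estimate

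*Protocol*

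**What the plan says.** Three parts of the protocol bear on this.

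**Section 8.3.3 (primary outcome).** The principal analysis is fixed as follows: "All principal analyses will be complete case, intention to treat". Three further steps concern missing data:
- A look at predictors: "We will also investigate baseline variables associated with missing outcome data for the primary outcome".
- The next sentence: "We will carry out mediation analyses to examine the influence of missingness". No mediator, outcome model or assumption is given.
- For the effect on the primary objective, "threshold analyses which will impute a poor outcome for missing pregabalin patients while assuming an average outcome for missing control patients".

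**Section 8.3.4 (withdrawal phase).** Here the wording is softer: "supportive analyses to examine the likely impact of attrition including the potential use of mediation analyses and joint models".

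**Section 8.3.1.** The SAP is to have a section headed "Analysis of Primary and Secondary Outcomes (including statistical models and method of dealing with missingness"). The SAP is not among the documents available.

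Two other statements show which intermediate variables are observed. Section 5.1.2 lists "Anxiety scores (GAD7) at week 3, week 6, week 26 and week 30", and section 4.2.4 says: "Participants who discontinue study medication will be invited to all follow up assessments".

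**The concern.** A mediation analysis splits a treatment effect into a part that passes through an intermediate variable and a part that does not. To do so it needs the outcome at different values of that variable. The mediation sentence directly follows one on missing primary outcome data, so its natural reading makes missingness the intermediate variable and week-12 GAD-7 the outcome. The outcome is then never seen at one of the mediator's two values.

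At stake is what a reader may conclude from the check. The principal analysis is complete case, and section 8.3.6 confirms that nothing will be imputed in it. If mediation does not address missing outcomes, what remains is a description of baseline predictors and a threshold analysis described in one direction only. A mediation result reported under this sentence could be taken as support for the complete-case estimate that it does not give.

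**Working it through.** **1. The protocol's own figures on attrition (section 8.1).** Inputs: difference 1.6 points, effective SD 4.9, 5% significance (two-sided assumed), 90% power, 20% attrition.
- n per group = 2 × (1.960 + 1.282)² × 4.9² / 1.6² ≈ 197.1, so 198. With the unrounded SD, 5.6 × √(1 − 0.47²) = 4.943, it is 201. The stated 199 lies between these.
- 199 / 0.80 = 248.75, so 249 per group and 498 in total, as stated.
- At 20% attrition, 0.20 × 498 = 99.6, so about 100 participants would have no week-12 GAD-7.

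These figures reproduce and are not in dispute.

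**2. Missingness as mediator.** Let A be arm, X baseline GAD-7, R = 1 if week-12 GAD-7 is missing, and Y week-12 GAD-7.
- Mediator model: R on A and X. It is fitted in all randomised participants, so the arm-to-missingness path can be estimated.
- Outcome model: E[Y] = b0 + b1·A + b2·X + b3·R. It can be fitted only where Y is observed, that is, where R = 0. The R column is then all zeros and b3 drops out.
- The indirect effect combines the arm-to-missingness path with b3, so it is not identified without an assumption that the data cannot test.

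**3. Rank check.** Data were simulated for 498 participants with about 20% missing, which left 396 observed outcomes.

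| Specification | Rows | Columns | Rank |
|---|---|---|---|
| Mediator = week-12 missingness | 396 | 4 | 3 |
| Same, with arm interaction | 396 | 5 | 3 |
| Mediator = treatment discontinuation | 396 | 4 | 4 |
| Mediator = week-6 GAD-7 | 396 | 4 | 4 |
| Mediator = missed week-6 visit | 396 | 4 | 4 |
| Missingness as the dependent variable | 498 | 4 | 4 |

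**4. What the full-rank versions answer.**
- Discontinuation as mediator: Table 5 gives people who stop medication but stay in the trial a treatment policy. The model therefore describes how the effect arises, not what absent scores do to it.
- Week-3 or week-6 GAD-7, or an earlier missed visit, as mediator: the outcome model is still fitted only in people with a week-12 score. By itself it says nothing about the others.
- Missingness as the dependent variable: this shows whether attrition differs by arm. It does not measure bias in the treatment difference.

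**5. The quantity that matters.** Assume a complete-case difference of −1.6 points, 20% missing in each arm, and missing controls like observed controls. Let d be how much worse missing pregabalin participants are than observed ones. The overall difference is −1.6 + 0.2d:
- d = 0 gives −1.6
- d = 4 gives −0.8
- d = 8 gives 0

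The observed scores do not determine d. The threshold analysis assumes values for it; a model with missingness as mediator cannot estimate it. This raw-scale illustration applies to any missing-data problem of this size and does not measure the effect of the mediation sentence.

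**The case against.** The strongest reply is that the protocol never says missingness is the mediator. Several mediators are observed and estimable, section 8.3.6 says mechanisms of missingness will be explored, and modelling detail is assigned to the SAP. This stands in part. A reader might infer from section 8.3.3 that the planned analysis cannot be estimated and gives no information. The document does not support that: no mediator is fixed, and even with week-12 missingness as mediator the arm-to-missingness path can be estimated. Deferral to the SAP does not remove the point, however. Section 8.3.3 already names a method and a purpose, and the estimable versions do not serve that purpose.

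Second, robustness does not rest on mediation. The threshold analysis is the step tied to the primary objective, and it probes outcomes missing not at random. This stands, and it limits the consequence. That analysis is described in one direction only, so it does not make a further check redundant.

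Third, imputation and weighting cannot estimate d either. This is correct. Both assume missing at random given the variables used, so they belong beside the threshold analysis and cannot replace it.

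Fourth, section 8.3.4 mentions only potential use, alongside joint models, and stopping study medication is an observable intermediate in that phase. This stands: section 8.3.4 needs a restriction on how mediation is used, not removal of it.

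**Conclusion.** The point holds in limited form. Section 8.3.3 commits to mediation as a way to examine missing primary outcome data without naming mediator or outcome. If week-12 missingness mediates week-12 GAD-7, the mediator-to-outcome path is not identified. If an observed variable is the mediator, the analysis can be run but does not show how missing outcomes affect the treatment estimate.

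The consequence is confined to a supportive analysis. About 100 of 498 participants would be affected at the planned 20%, and section 8.1 expects better follow-up than that. A reader might take the shifts of 0.8 and 1.6 points in the illustration (from −1.6 to −0.8 and to 0) as the cost of choosing mediation. They are not: they rest on assumed values of d and on raw points, whereas the primary endpoint is log GAD-7, and they would be the same if the mediation sentence were deleted. The primary analysis, sample size, alpha and power do not change.

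**What to change.** In section 8.3.3, stop using mediation as the check on missing week-12 GAD-7. Replace it with a sensitivity analysis on the log GAD-7 scale, by multiple imputation within arm or by inverse-probability-of-observation weighting. Use the baseline predictors of missingness that the section already plans to investigate, together with the week-3 and week-6 GAD-7. State that this analysis assumes missing at random, and keep the threshold analysis for departures from that assumption. Section 9.2 already plans multiple imputation as a sensitivity analysis for the economic evaluation, so the method is not new to the trial.

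If mediation is kept in section 8.3.3 or 8.3.4, restrict it to a named, observed mediator and present it as an analysis of mechanism, not as evidence of robustness to missing data. Keep the joint model for the ~30-week comparison.

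The cost is a wording change in the protocol and SAP and one extra sensitivity run. No new data are needed.
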